9.2.1. Incidence of Adverse Events

An overview summary of the following TEAE categories for the prime and boost analysis period will be provided separately:

- Any TEAE

- Any TEAE related to vaccination
- Any severe TEAE
- Any serious TEAE
- Any serious TEAE related to vaccination
- Any TEAE Leading to Withholding of Day 85 Vaccination
- Any TEAE leading to study discontinuation
- Any TEAE leading to death

9.2.2. Severity of Adverse Event

TEAEs will be rated as Mild, Moderate, or Severe based on the following criteria:

- Mild: These events require minimal or no treatment and do not interfere with the subject's daily activities.
- Moderate: These events result in a low level of inconvenience or concern with the therapeutic measures. Moderate events may cause some interference with normal functioning.
- Severe: These events interrupt a subject's usual daily activity and may require systemic drug therapy or other treatment. Severe events are usually incapacitating.

If a subject reports multiple occurrence of a specific event, the subject will be counted only once by the maximum severity. If the severity is missing for one or more of the occurrences, the maximum severity of the remaining occurrences will be used.

9.2.3. Relationship of Adverse Events to Study Vaccination

Study treatment related TEAEs will be summarized by SOC and PT as well as maximum severity grade. Study vaccination related AEs are those with a relationship to study treatment of 'Related' based on the eCRF page. AEs assessed as 'Not Related' will be considered unrelated for reporting purpose. Missing relationship will be counted as related to study vaccination.

9.2.4. Serious Adverse Events

Serious AEs are those identified on the eCRF as meeting the protocol defined serious criteria. Serious TEAEs will be summarized by SOC and PT and severity for each period.

A by-subject listing will also be provided.

9.2.5. Suspected Unexpected Serious Adverse Reaction

Suspected Unexpected Serious Adverse Reaction (SUSAR) will be summarized by SOC and PT, and maximum severity for each period. For this study any SAE related to vaccination will be a SUSAR by definition and therefore these two terms will be provided in a single output.

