1.3.5 Boostrix Risks to Study Subjects

The risks of Boostrix administration are expected to be minimal and clinically manageable. Local adverse reactions include pain, redness, swelling, and injected arm circumference increase. General adverse reactions include headache, fatigue, gastrointestinal symptoms, and fever.

The tip caps of the prefilled syringes contain natural rubber latex which may cause allergic reactions.

If Guillain-Barré syndrome occurred within 6 weeks of receipt of a prior vaccine containing tetanus toxoid, the risk of Guillain-Barré syndrome may be increased following a subsequent dose of tetanus toxoid-containing vaccine, including Boostrix.

Syncope can occur in association with administration of injectable vaccines, including Boostrix. Syncope can be accompanied by transient neurological signs such as visual disturbance, paresthesia, and tonic-clonic limb movements. Procedures for administration should be in place to avoid falling injury and to restore cerebral perfusion following syncope.

Progressive or unstable neurologic conditions (eg, cerebrovascular events and acute encephalopathic conditions) are reasons to defer vaccination with a pertussis-containing vaccine, including Boostrix. It is not known whether administration of Boostrix to subjects with an unstable or progressive neurologic disorder might hasten manifestations of the disorder or affect the prognosis. Administration of Boostrix to subjects with an unstable or progressive neurologic disorder may result in diagnostic confusion between manifestations of the underlying illness and possible adverse effects of vaccination.

Persons who experienced an Arthus-type hypersensitivity reaction following a prior dose of a tetanus toxoid-containing vaccine usually have a high serum tetanus antitoxin level and should not receive Boostrix or other tetanus toxoid-containing vaccines unless at least 10 years have elapsed since the last dose of tetanus toxoid-containing vaccine.

As with any vaccine, if administered to immunosuppressed individuals, including individuals receiving immunosuppressive therapy, the expected immune response may not be obtained.

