6.3.5.6 Reporting Serious Adverse Events

Any AE that meets SAE criteria ([Section 6.3.5.2](#)) must be reported to the CRO immediately (ie, within 24 hours) after the time site personnel first learn about the event. The contact information to be used for SAE reporting will be provided to the CRO and the CRO will oversee the SAE reporting.

6.3.5.7 Suspected Unexpected Serious Adverse Reactions and Nonserious Adverse Events of Special Interest

The sponsor will promptly evaluate all SUSARs and nonserious AEs of special interest against cumulative product experience to identify and expeditiously communicate possible new safety findings to investigators, institutional review boards (IRBs), and applicable health authorities based on applicable legislation.

To determine reporting requirements for single AE cases, the sponsor will assess the expectedness of these events using the following reference documents:

- study vaccination investigator's brochure

The sponsor will compare the severity of each SUSAR and the cumulative event frequency reported for the study with the severity and frequency reported in the applicable reference document.

Reporting requirements will also be based on the investigator's assessment of causality and seriousness, with allowance for upgrading by the sponsor as needed.

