7.7.5 Analysis of Secondary Safety Endpoints

Adverse events (eg, treatment-emergent AEs, SAEs, and SUSARs) will be coded by MedDRA for preferred term and system organ class.

Serious AEs will be reported by detailed listings showing the event description, MedDRA preferred term and system organ class, relevant dates (study vaccinations and AEs), severity, relatedness, and outcome for each event. Any SAE attributed to vaccination will be classified as a SUSAR. Nonserious unsolicited AEs will be summarized as number and percentage of subjects reporting at least one event in each MedDRA preferred term and system organ class, and cross tabulated by severity and relationship to study product.

Measurements of vital signs will be statistically described, and categorical severity scores of vital signs will be summarized in counts and percentages of subjects by treatment arm. Change from baseline will be expressed where applicable.

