4.6. Handling of Missing Data

Data will be presented in the listings as reported. For summaries and analysis, the following conventions apply.

Immunogenicity Data

No Imputation methods will be used for missing immunogenicity data and all analyses will be based on complete records only.

Any pertussis antigen specific antibody titer (PT, FHA, PRN, FIM 2/3, or BPZE1 whole cell extract) from either serum or nasal mucosal sample that is below the minimal limit of assay detection will be imputed with a value equal to half of the minimal limit of assay detection of the antigen specific antibody titer.

Adverse Event Data

Missing date will be imputed as described in [Appendix 13.4](#). Missing information regarding ‘relationship to study vaccine’ or ‘severity’ will be imputed as related to study vaccine and severe, as the worst-case scenario.

Prior/Concomitant Medication Data

Missing date will be imputed as described in [Appendix 13.4](#).

5. Subject Disposition

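### The SUSAR summary drops the 'unexpected' criterion: Protocol 7.7.5 and SAP 9.2.5 count every related SAE, including one with a blank causality field, while Protocol 6.3.5.7 calls for an expectedness assessment

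*SAP*

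**What the plan says.** Three rules bear on what the SUSAR summary will contain.

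- **Tabulation.** Protocol 7.7.5: "Any SAE attributed to vaccination will be classified as a SUSAR". SAP 9.2.5 implements this: "For this study any SAE related to vaccination will be a SUSAR by definition". It then reports both categories together in one table. Neither section mentions expectedness or gives a reason for leaving it out.
- **Expectedness.** Protocol 6.3.5.7, in setting reporting requirements for single cases, says that "the sponsor will assess the expectedness of these events using the following reference documents". The list that follows has one entry: "study vaccination investigator's brochure". The same section has the sponsor compare severity and cumulative frequency with that document.
- **Missing causality.** Under SAP 4.6 a missing relationship or severity "will be imputed as related to study vaccine and severe, as the worst-case scenario". SAP 9.2.3 repeats the rule for relationship: "Missing relationship will be counted as related to study vaccination". Neither section exempts serious events.

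SUSARs are named as an example within the unsolicited-AE secondary endpoint (Protocol 2.5.4, SAP 3.2.2.4).

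**The concern.** A SUSAR has three elements: serious, suspected (related) and unexpected. The tabulation rule tests the first two and assumes the third. For BPZE1 that may do little harm, since Protocol 1.1 reports no vaccine-related SAEs in two Phase 1 studies. The argument does not carry over to Boostrix, a licensed product whose known risks are set out in Protocol 1.3.5, for example: "Syncope can occur in association with administration of injectable vaccines, including Boostrix". A related SAE of a kind described there would be shown as unexpected whatever the sponsor had decided.

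The imputation rule adds a second route. A blank causality field becomes related, and related becomes SUSAR, so an event that nobody judged to be either suspected or unexpected is counted as both. At stake is whether the SUSAR count in the clinical study report agrees with the sponsor's own case assessments, and whether the comparator is presented fairly.

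**Working it through.** The documents state no SUSAR count or expected rate, so there is no figure to reproduce. The check is to follow each type of SAE through the rules.

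| SAE | Under Protocol 6.3.5.7 | Under Protocol 7.7.5 / SAP 9.2.5 | Agree? |
|---|---|---|---|
| Judged related; sponsor finds it unexpected | SUSAR | SUSAR | Yes |
| Judged related; sponsor finds it expected | Not a SUSAR | SUSAR | No |
| Relationship blank | No recorded suspicion | Related by SAP 4.6 and 9.2.3, hence SUSAR | No |
| Judged not related | Not a SUSAR | Not a SUSAR | Yes |

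The rules part in rows two and three.

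**Can row two occur?** Protocol 1.3.5 describes latex allergy and syncope with tonic-clonic movements among the Boostrix risks. The SAE examples in Protocol 6.3.5.2 include allergic bronchospasm and convulsions, so serious forms of related kinds are conceivable. Whether a given event is expected cannot be settled from the documents. Section 6.3.5.7 names only an investigator's brochure, and the only brochure in the protocol's reference list is the one for BPZE1. Protocol section 8 mentions package inserts as pre-enrolment reading, not as an expectedness reference.

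**Can the planned outputs separate the rows?** Only in part. SAP 4.6 shows listing data as reported, so a blank relationship (row three) would be visible in the SAE listing. The SAE listing contents in Protocol 7.7.5 do not include expectedness, so row two could not be told from row one. The definition of related in Protocol 6.3.5.9 refers to study vaccination as a whole and does not separate BPZE1 from Boostrix.

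**Illustration of size.** Assume no SUSAR on the sponsor's assessment and one SAE from row two or three. The exact (Clopper-Pearson) 95% limits for x events in n subjects are: lower = the 0.025 quantile of Beta(x, n − x + 1), upper = the 0.975 quantile of Beta(x + 1, n − x). For x = 0 the lower limit is 0 and the upper is 1 − 0.025^(1/n); for n = 100 this gives 3.62%.

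| Group | n | 0 events | 1 event |
|---|---|---|---|
| Boostrix prime (C+D) | 100 | 0% (0 to 3.62) | 1/100 = 1.0% (0.03 to 5.45) |
| One Boostrix arm (C or D) | 50 | 0% (0 to 7.11) | 1/50 = 2.0% (0.05 to 10.65) |
| All subjects | 300 | 0% (0 to 1.22) | 1/300 = 0.33% (0.01 to 1.84) |

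The single event is an assumption. The table shows what one label does at the planned sizes, not what is likely to happen.

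**The case against.** The case against is substantial, and much of it stands.

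- **The SAP follows the protocol.** A reader might infer that the SAP departed from it. It did not: SAP 9.2.5 carries out Protocol 7.7.5. The conflict is between two sections of the protocol, and the SAP inherits it.
- **The sections serve different purposes.** Section 6.3.5.7 governs reporting of single cases; 7.7.5 and SAP 9.2.5 set a table convention. A reader might infer that expedited reporting is wrong. Nothing shows that, because the sponsor's assessment still takes place.
- **Listed does not mean expected.** A reader might infer that every serious Boostrix reaction of a kind named in 1.3.5 would be misclassified. The documents do not support this. Section 1.3.5 is a risk narrative, not the reference document, and under 6.3.5.7 a listed kind of event could still be unexpected if more severe or more frequent than described.
- **Missing causality on an SAE should be rare.** Protocol 6.3.5.5 requires every AE to be assessed for relationship, SAEs go to the CRO within 24 hours, and the medical monitor reviews them in real time. A blank would show in the listings, and the imputation errs towards showing harm.
- **Part of the remedy exists.** SAP 9.2.1 already has a row for serious TEAEs related to vaccination, and SAP 9.2.5 says openly that the two terms share one output.
- **SUSARs are not an endpoint of their own.** They are an example within the unsolicited-AE endpoint. No hypothesis is tested, and the halting rule in Protocol 6.4 uses related SAEs, not SUSARs.

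These points limit the size of the problem but do not remove it. Disclosing that two terms share an output does not make them the same. Worst-case imputation suits a table of related events; it is not a basis for a label that requires a judgement.

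**Conclusion.** The rule is wrong as written, with a narrow effect. Protocol 7.7.5 and SAP 9.2.5 conflict with Protocol 6.3.5.7. The tabulation rule omits expectedness and, combined with SAP 4.6 and 9.2.3, can place an SAE of unassessed causality under the SUSAR label.

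The consequence is confined to the SUSAR summary and its title. Non-serious reactions, the related-SAE count, halting and expedited reporting are not shown to be affected. Few events are likely, but from a base of zero one is enough to change the summary. The issue matters mainly for Boostrix, planned for 100 of about 300 subjects. That is the number exposed, not the number expected to be misclassified.

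The conclusion assumes that at least one related SAE would be judged expected, or that at least one SAE has no causality entry at analysis. The first also depends on an expectedness reference for Boostrix, which the protocol does not name. Without one, deriving SUSARs from 6.3.5.7 would not by itself settle how a related Boostrix SAE should be labelled.

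**What to change.** 1. Reconcile Protocol 6.3.5.7, Protocol 7.7.5 and SAP 9.2.5 so that one definition of SUSAR applies.
2. Title the combined output as SAEs related to vaccination, and keep the worst-case imputation of relationship there.
3. Within that output, flag SUSARs from the sponsor's recorded expectedness decision.
4. In Protocol 6.3.5.7, name the reference document for expectedness separately for BPZE1 and for Boostrix.
5. Query any SAE with missing causality before database lock. If it stays missing, show it on its own line, so that imputation alone never creates a SUSAR.

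The cost is wording changes and one added flag. The documents do not show where the expectedness decision is held, so confirm that it can be transferred to the analysis data. No safety information is lost, because every related SAE stays in the table.

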9.2.6. Adverse Events Leading to Withholding of Day 85 Vaccination

TEAEs leading to Withholding of Day 85 Vaccination will be summarized by SOC and PT for periods Day 1 to Day 84.

A by-subject listing will also be provided.

9.2.7. Adverse Events Leading to Study Discontinuation

TEAEs leading to study discontinuation will be summarized by SOC and PT for periods (for periods (Day 1- Day 84, Day 85-Day 113 and Day 114 through EOS).

A by-subject listing will also be provided.

9.2.8. Death

TEAEs leading to death will be summarized by SOC and PT for periods (Day 1 to Day 113 and Day 114-EOS).

A by-subject listing will also be provided for all adverse events leading to death.

9.3. Clinical Laboratory Evaluations

For those subjects in the Safety lead-in analysis set, laboratory results will be summarized for serum chemistry, hematology and coagulation as observed values and change from baseline on Day 8/Visit 2 following prime vaccination and Day 92/Visit 6 following boost vaccination using descriptive statistics (mean, median, standard deviation, min, max). Laboratory results will also be classified by toxicity score based on the US Food and Drug Administration (FDA) toxicity scoring system (Appendix 13.2). Counts and percentages of subjects will be summarized by toxicity grade on Day 8 and 92. In the case of no toxicity classification the score of 0 will be assigned.

For those subjects in the safety set, baseline value will be summarized for serum chemistry, hematology and coagulation using descriptive statistics (mean, median, standard deviation, min, max).

Summaries will be presented based on treatment arms of BPZE1 prime with BPZE1 boost (A), BPZE1 prime with no boost (B), Total Post BPZE1 (A+B), Boostrix prime with BPZE1 boost (C) and Boostrix prime with no boost (D), Boostrix prime (C+D), Total Post Booster BPZE1 (A+C), and Total Post Placebo Boost (B+D), Total Any BPZE1 Exposure (A+B+C) and Total (A+B+C+D).

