2.4.2 Primary Safety Endpoints

The primary safety endpoints of this study are:

- Solicited AEs (local, nasal/respiratory, and systemic reactogenicity events) for 7 days following each vaccination by severity score, duration, and peak intensity. Local reactogenicity will only be monitored following the IM vaccination.
- Safety laboratory results (serum chemistry, hematology, coagulation) by US Food and Drug Administration (FDA) toxicity score (change from baseline or absolute toxicity score) in the safety lead-in cohort at Day 8 following each vaccination. In the case of no toxicity classification, the score of 0 will be assigned.

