6.7 Sample Collections

Procedures for the handling and processing of biological samples are provided in the Laboratory Manual or the Site Manual.

The hematology, coagulation, and chemistry laboratory analyses will be performed at a central laboratory. Laboratory data will be graded according to the FDA Toxicity Grading Scale (Table 13-2) and will be adjusted according to local laboratory reference ranges.

The samples collected for immunogenicity (B and T cell) testing and pertussis culture will be stored in appropriate conditions as specified in the Laboratory Manual until shipped for testing at a facility designated by the sponsor.

Subjects will be asked to provide a signed informed consent for the use of samples for further pertussis-specific testing or assay development. Aliquots of collected samples from this study may be retained for additional testing of antigens specific to *B. pertussis* for a maximum of 10 years (starting from the date at which the last subject had the last study visit), unless local rules, regulations, or guidelines require different timeframes or different procedures, in accord with subject consent. Testing for colonization using *B. pertussis* culture following the primary vaccination and post-boosting vaccination will also occur.

7 Statistical and Analytical Plan

The primary objectives of this study are to assess nasal mucosal immune response S-IgA following intranasal vaccination with BPZE1 (10^9 CFU) when used as a single (eg, prime) or 2-dose (eg, prime + boost) series and reactogenicity (all) and specific safety laboratory parameters (safety lead-in cohort only) following intranasal vaccination with BPZE1 (10^9 CFU), in healthy volunteers 18 to 50 years of age. This study is designed as a randomized, placebo-controlled, observer-blinded clinical trial evaluating the safety and immunogenicity of 1 or 2 doses of 10^9 CFU of BPZE1 delivered by intranasal VaxINator device or Boostrix delivered by IM injection. To maintain the blind, placebo vaccination via IM and intranasal routes will be included.

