3.2.1.2. Primary Safety Endpoints

The primary safety endpoints of this study are:

- Solicited AEs (local, nasal mucosal secretion, and systemic reactogenicity events) for 7 days following each vaccination by severity score, duration, and peak intensity. Local reactogenicity will only be monitored following the IM vaccination.
- Safety laboratory results (serum chemistry, hematology, coagulation) by US Food and Drug Administration (FDA) toxicity score (change from baseline or absolute toxicity score) in the safety lead-in cohort at Day 8 following each vaccination. In the case of no toxicity classification the score of 0 will be assigned.

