The dose of BPZE1 active ingredient will be administered to the subject within 60 minutes of removal from the freezer. One milliliter of WFI will be used to reconstitute the 1 mL vial of lyophilized BPZE1, but only 0.8 mL of vaccine will be withdrawn for administration into both nostrils. Following reconstitution, the VaxINator will be attached to the syringe, and 0.4 mL volume will be administered to each nostril. In the case of placebo nasal vaccination, a similar volume of WFI will be reconstituted into a vial containing only lyophilized buffer, followed by 0.4 mL volume administered into each nostril with the vaccinator. The VaxINator provides a uniform, controlled delivery, which allows the vaccinator to accurately deliver 0.4 mL of vaccine to the initial nostril and then administer the remaining 0.4 mL to the opposite nostril.

The study vaccine will be labeled according to manufacturer specifications and include the statement “Caution: New Drug – Limited by Federal Law to Investigational Use.”

4. General Statistical Considerations

No formal hypothesis will be tested in this study. Statistical analysis will be performed using SAS software Version 9.4. Continuous variables will be summarized using the mean, 2-sided 95% CI of the mean, SD, median, minimum value, and maximum value. Categorical variables will be summarized using frequency counts and percentages, as well as 2-sided 95% CI for proportions computed using the Clopper-Pearson method. Graphics of reverse cumulative distribution of anti-pertussis antibody titers will be generated through Day 113 for the primary database lock and assessing serum and mucosal pertussis antigen response. .

For summary precision, mean and median will have one more decimal place than the reported value, SD will have two more decimal places than the reported value, minimum and maximum will have the same decimal place as the reported value. Percentages and 95% CI will have one decimal place.

Where applicable, data analyses will be conducted for the prime period (prior to boosting) and boost period (at or post boosting). Pre-prime and pre-boost baseline will be used for summaries based on the Immunogenicity Analysis Set.

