4.3.5. Safety Lead-in Analysis Set

The Safety Lead-in Analysis Set will consist of the first 48 subjects who have been randomized to the study. Subjects will be classified according to the vaccine received and group into BPZE1 prime (10^7 CFU), BPZE1 prime (10^9 CFU) and Boostrix prime arms

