13.2. FDA Table for Laboratory Grading

Table 12-2 Laboratory Abnormalities

Serum ^a	Mild (Grade 1)	Moderate (Grade 2)	Severe (Grade 3)	Potentially Life Threatening (Grade 4) ^b
Sodium – hyponatremia (mEq/L)	132-134	130-131	125-129	< 125
Sodium – hypernatremia (mEq/L)	144-145	146-147	148-150	> 150
Potassium – hyperkalemia (mEq/L)	5.1-5.2	5.3-5.4	5.5-5.6	> 5.6
Potassium – hypokalemia (mEq/L)	3.5-3.6	3.3-3.4	3.1-3.2	< 3.1
Glucose – hyperglycemia Random(mg/dL)	110-125	126-200	> 200	Insulin requirements or hyperosmolar coma
Blood Urea Nitrogen (mg/dL)	23-26	27-31	> 31	Requires dialysis
Creatinine (mg/dL)*	1.5-1.7	1.8-2.0	2.1-2.5	> 2.5 or requires dialysis
Calcium – hypocalcemia (mg/dL)	8.0-8.4	7.5-7.9	7.0-7.4	< 7.0
Calcium – hypercalcemia (mg/dL)	10.5-11.0	11.1-11.5	11.6-12.0	> 12.0
Albumin – hypoalbuminemia (g/dL)	2.8-3.1	2.5-2.7	< 2.5	--
Total Protein – hypoproteinemia (g/dL)	5.5-6.0	5.0-5.4	<5.0	--
Liver Function Tests –ALT, AST increase by factor*	1.1-2.5 × ULN	2.6-5.0 × ULN	5.1-10 × ULN	> 10 × ULN
Bilirubin – when accompanied by any increase in liver function test increase by factor*	1.1-1.25 × ULN	1.26-1.5 × ULN	1.51-1.75 × ULN	> 1.75 × ULN
Bilirubin – when liver function test is normal; increase by factor*	1.1-1.5 × ULN	1.6-2.0 × ULN	2.0-3.0 × ULN	> 3.0 × ULN
Hematology ^a	Mild (Grade 1)	Moderate (Grade 2)	Severe (Grade 3)	Potentially Life Threatening (Grade 4) ^b
Hemoglobin (Female)(gm/dL)*	11.0-12.0	9.5-10.9	8.0-9.4	< 8.0
Hemoglobin (Female) change from baseline value (gm/dL)	Any decrease - 1.5	1.6-2.0	2.1-5.0	> 5.0
Hemoglobin (Male)(gm/dL)*	12.5-13.5	10.5-12.4	8.5-10.4	< 8.5
Hemoglobin (Male) change from baseline value (gm/dL)	Any decrease - 1.5	1.6-2.0	2.1-5.0	> 5.0
WBC Increase(cell/mm ³)*	10,800-15,000	15,001-20,000	20,001-25,000	> 25,000
WBC Decrease (cell/mm ³)*	2,500-3,500	1,500-2,499	1,000-1,499	< 1,000
Platelets Decreased - cell/mm ³ *	125,000 – 140,000	100,000 – 124,000	25,000 – 99,000	< 25,000
Prothrombin time – increase by factor*	1.0-1.10 × ULN	1.11-1.20 × ULN	1.21-1.25 × ULN	> 1.25 × ULN

partial thromboplastin time – increase by factor *	1.0-1.2 × ULN	1.21-1.4 × ULN	1.41-1.5 × ULN	> 1.5 × ULN
---	---------------	----------------	----------------	-------------

Abbreviations: ALT, alanine aminotransferase; AST, aspartate aminotransferase; ULN, upper limit of normal; WBC, white blood cell.

*Screening labs with toxicity scores greater than 1 are exclusion criteria for the full cohort only (greyed line items).

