13.3. FDA Table for Vital Sign Grading – Vital Sign Abnormality

Table 12-3 Vital Sign Abnormality

Vital Signs ^a	Mild (Grade 1)	Moderate (Grade 2)	Severe (Grade 3)	Potentially Life Threatening (Grade 4)
Fever (°F) ^b	100.4 – 101.1	101.2 – 102.0	102.1 – 104	>104
Tachycardia (beats per minute)	101 – 115	116 – 130	>130	Emergency room visit or hospitalization for arrhythmia
Bradycardia (beats per minute) ^c	50 – 54	45 – 49	<45	ER visit or hospitalization for arrhythmia
Hypertension (systolic) (mm Hg)	141 – 150	151 – 155	>155	ER visit or hospitalization for malignant hypertension
Hypertension (diastolic) (mm Hg)	91 – 95	96 – 100	>100	ER visit or hospitalization for malignant hypertension
Hypotension (systolic) (mm Hg)	85 – 89	80 – 84	<80	ER visit or hospitalization for hypotensive shock

Note: Grade 0 will be the classification if the observation is less than a Grade 1. Respiratory rate was removed from the FDA table for vital sign grading as this is not a parameter being measured in this study.

- a. Subject should be at rest for all vital sign measurements.
- b. Oral temperature; no recent hot or cold beverages or smoking.
- c. When resting heart rate is between 60 to 100 beats per minute. Use clinical judgement when characterizing bradycardia among some healthy subject populations, for example, conditioned athletes.

Source: [DHHS 2007](#).

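### The laboratory score-0 rule has no below-Grade-1 limit and no rounding convention, so an unrounded result lying between two grade bands would be tabulated as Grade 0

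*SAP*

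**What the plan says.** The laboratory toxicity score on Day 8 after each vaccination is one of the items that SAP 3.2.1.2 lists after "The primary safety endpoints of this study are". Protocol 2.4.2 says the same and adds: "In the case of no toxicity classification, the score of 0 will be assigned". Protocol 7.1 repeats this. SAP 9.3 carries the rule into the analysis ("In the case of no toxicity classification the score of 0 will be assigned") and counts subjects by grade on Days 8 and 92. Protocol 7.7.2 also plans shifts in grade from baseline.

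The population is small: "The Safety Lead-in Analysis Set will consist of the first 48 subjects who have been randomized to the study" (SAP 4.3.5).

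For vital signs, SAP Appendix 13.3 defines the zero category differently: "Grade 0 will be the classification if the observation is less than a Grade 1". The same note stands under the reactogenicity grading table in both documents. The laboratory table has no such note.

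The SAP's precision conventions (section 4, General Statistical Considerations) cover summary statistics only, for example "Percentages and 95% CI will have one decimal place". Protocol 6.7 says that laboratory grading "will be adjusted according to local laboratory reference ranges", which is not a rounding rule either.

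**The concern.** A result can lack a classification in three ways: it does not reach Grade 1, its test or direction has no scale, or it falls between two printed bands. The rule gives 0 in all three. In the third case the result is more abnormal than Grade 1's outer limit, and scoring it 0 ranks it below milder results. A program that assigns a grade when a value lies in a band, and 0 otherwise, would follow the SAP exactly and make this error silently.

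At stake are the grade tables for a primary safety endpoint, the shift tables, and the Day 8 grade tables that SAP section 10 sends to the Safety Monitoring Committee before full enrolment. The lead-in groups have 16 subjects each (10^7 CFU, 10^9 CFU, and Boostrix as 8 + 8), so one misgraded subject is 1/16 = 6.3% of a group.

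**Working it through.** The plan states no figure to reproduce. The check is whether the bands in SAP Appendix 13.2 (identical in Protocol Table 13-2) cover every value between the first and last limits, and cover it once. The table has 23 rows. The two rows for haemoglobin change are identical, leaving 22 distinct sets of bands.

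**1. At printed precision.** Stepping through each set in units of its finest printed digit gives no gap in any of the 22. There is one overlap: bilirubin with normal liver tests has Grade 2 at 1.6–2.0 and Grade 3 at 2.0–3.0 × ULN.

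**2. With one more digit.** Every set has a gap at the Grade 1/2 boundary, the Grade 2/3 boundary or both. None has a gap at Grade 3/4, because the last category is open-ended.

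**3. Concrete results.** For tests graded by multiples of ULN, ratio = result / ULN, which usually carries extra digits. The documents give no ULN and no reporting resolution. Those below are assumptions: ALT in whole U/L, clotting times to 0.1 s, bilirubin to 0.1 mg/dL.

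| Test (assumed ULN) | Last value in lower band | No band | First value in upper band |
|---|---|---|---|
| ALT (40 U/L) | 100 = 2.500, Grade 1 | 101–103 = 2.525–2.575 | 104 = 2.600, Grade 2 |
| ALT (40 U/L) | 200 = 5.000, Grade 2 | 201–203 = 5.025–5.075 | 204 = 5.100, Grade 3 |
| Prothrombin time (12.5 s) | 13.7 = 1.096, Grade 1 | 13.8 = 1.104 | 13.9 = 1.112, Grade 2 |
| Prothrombin time (12.5 s) | 15.0 = 1.200, Grade 2 | 15.1 = 1.208 | 15.2 = 1.216, Grade 3 |
| Bilirubin, normal liver tests (1.2 mg/dL) | 1.8 = 1.500, Grade 1 | 1.9 = 1.583 | 2.0 = 1.667, Grade 2 |

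With a bilirubin ULN of 1.0 mg/dL no reportable value is lost (1.5 is Grade 1, 1.6 is Grade 2).

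Tests graded on absolute values are affected only if reported more finely than the table:
- Creatinine to two decimals loses 1.71–1.79 and 2.01–2.09 mg/dL, which is 18 of 101 values from 1.50 to 2.50. To one decimal it loses 0 of 11.
- Gaps exist on the low side too. Platelet Grade 2 is "100,000 – 124,000" and Grade 1 starts at 125,000, so 124,001–124,999 has no band. Reporting in whole thousands avoids this.

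**4. Share of possible values.** Share = values with no band / reportable values from the Grade 1 lower limit to the Grade 3 upper limit, inclusive.
- ALT: ULN 35, 6/312 = 1.9%; ULN 40, 6/357 = 1.7%; ULN 55, 10/490 = 2.0%.
- Prothrombin time: ULN 12.5, 2/32 = 6.3%; ULN 14.5, 2/37 = 5.4%.
- Partial thromboplastin time: ULN 34, 6/171 = 3.5%; ULN 40, 6/201 = 3.0%.

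These are shares of possible values, not of expected subjects.

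**5. After rounding.** Rounding to the finest digit printed in the row (0.1 for ALT, AST and bilirubin with normal liver tests; 0.01 for both clotting times and for bilirubin with raised liver tests) leaves no value between bands for any ULN tried. The overlap at bilirubin 2.0 × ULN remains.

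**The case against.** The strongest reply is that this is one literal reading of a sentence with a natural meaning. Both documents define Grade 0 elsewhere as less than Grade 1, and the authors very probably meant that here. The phrase may also have been written for tests with no scale, since the white-cell differential and low glucose are measured but have no bands. The bands are contiguous at printed precision, and the table is described as a guideline to be adapted to laboratory ranges. All of this is fair, and it is why the point is minor. It does not remove the point, because the limit is written for the other two scales and missing from this one, and no grading precision is stated anywhere.

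Three stronger readings are tempting, and the documents do not support them.
- *Abnormal results are reported as normal.* Grade 0 is a score, and neither document calls it normal. SAP 9.3 also summarises observed values and change from baseline with minimum and maximum, and SAP 9.3.1 to 9.3.3 provide by-subject listings.
- *The same zero lets subjects past the screening exclusion or the Grade 3 adverse-event rule.* The score-0 sentence appears only with the lead-in endpoint and its summary. Exclusion criterion 25 and Protocol 6.3.4 and 6.6 use the table, or the grades it gives, but do not say that an unclassified value is 0.
- *A large share of creatinine values is lost.* The 18 of 101 depends wholly on two-decimal reporting.

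**Conclusion.** The point holds as a drafting defect with a small effect. As written, the rule gives Grade 0 to an unrounded result that falls between Grades 1 and 2 or between Grades 2 and 3. At a Grade 2/3 gap that is wrong whichever neighbouring grade is right. The bilirubin overlap at 2.0 × ULN does not depend on rounding at all.

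Few subjects can be affected. Scheduled post-vaccination laboratory tests are confined to 48 people, each with no screening grade above 1, and a result must land in a narrow interval. The size rests on assumed ULNs and reporting resolution. If the laboratory's grading already rounds to the table's precision, the between-band effect is nil and only the overlap is left.

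**What to change.** In SAP 9.3 and the laboratory table footnote:

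1. State that each result or ratio is rounded to the finest digit printed in its row before grading, and how ties are handled (ALT 102/40 = 2.55 is a tie), or write equivalent continuous cut-points. Rounding also acts at the ends of the scale: with ULN 40, ALT 43 (1.075) rounds to 1.1 and enters Grade 1, while 401 (10.025) rounds to 10.0 and no longer exceeds 10. If that is unwanted, cut-points are the cleaner choice.
2. Reserve 0 for results less abnormal than the Grade 1 bound.
3. Label results from tests or directions with no scale as not gradable.
4. Reconcile the Grade 2 and Grade 3 bilirubin bands at 2.0 × ULN so that one grade applies.
5. Use the same convention wherever the table is applied.

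The cost is one footnote and one programming rule. Item 3 departs from the protocol's literal sentence, so it should be recorded in SAP section 11, which at present declares no changes.
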